11.2. Analysis Sets

The Safety Analysis Set will include all enrolled subjects, defined as subjects deemed eligible for treatment at D0 in the SAD cohorts, and those randomized in the DB-RD cohorts, and those who continue into OL-RD from SAD cohorts. A Per Protocol (PP) Analysis Set, consisting of subjects who complete the study without major protocol deviations that could compromise PD or efficacy assessments may be analyzed as described in the SAP. The PK Analysis Set is a subset of subjects in the Safety Analysis Set who have at least 1 evaluable IP concentration. The PK Analysis Set will be used for the analysis of PK endpoints.

11.3. Planned Methods of Analysis

This section is a summary of the planned statistical analyses of the most important endpoints.

11.3.1. General Principles

A general description of the statistical methods to be used to analyze the study endpoints is outlined below. The analyses planned in this protocol will be expanded in the SAP to include detailed description of the analyses.

Descriptive statistics will be provided for selected demographics, safety, PK, and PD data. After review, data for subjects receiving placebo may be combined across all cohorts to form a pooled placebo group. If a sufficient number of subjects with different disease subtypes are enrolled, subgroup summaries by disease subtype will be provided. Continuous variables will be summarized by number of subjects and mean, SD and/or SE, median, minimum, and maximum values. Categorical variables will be summarized by number and percentage of subjects. Data will be summarized with descriptive statistics for the Screening Period for the DB-RD cohorts.

COVID-19 contingency measures and trial subjects affected by COVID-19 will be listed.

Although they are eligible, it is expected that few patients with GSD IIIb, IIIc, or IIId will enroll. Subjects with GSD IIIb/c/d will participate in all assessments, including muscle imaging and

function tests, and will be included in all safety analyses. Sensitivity analyses for cardiac and skeletal muscle endpoints may exclude patients with GSD IIIb/c/d as described in the SAP.

11.4. Safety Analyses

Safety variables including all AEs, SAEs, TEAEs, serious TEAEs, related TEAEs, safety laboratory assessments (full list available in [Appendix 3](#)), vital signs, weight, physical examination, clinical laboratory evaluations, and ECGs will be summarized for all subjects throughout the study and by treatment and cohort. Incidence and severity of IRRs and hypersensitivity reactions will also be summarized for all subjects throughout the study and by treatment and cohort. All AEs occurring from the onset of the study treatment infusion, and within 4 hours following the end of the infusion, regardless of the Investigator's assessment of whether or not the event was related to study drug administration will be considered an IRR.

All AEs will be coded according to the Medical Dictionary for Regulatory Activities (MedDRA) Version 23.0. The frequency and severity of all TEAEs, SAEs, and clinically relevant laboratory and ECG abnormalities will be reported by System Organ Class (SOC), by preferred term, and by relationship to study drug. All AEs reported with onset after the first dose of study drug (ie, TEAEs) will be included in the analysis. All SAEs will also be reported by relationship to study drug as reported by Investigator, seriousness, and outcome. For all AEs, SAEs, and treatment-related AEs, SAEs, the percentage of subjects who experienced at least 1 occurrence of the given event will be summarized for all subjects in the SAD cohorts and by treatment and cohort for the RD cohorts. Data summaries, listings, and narratives will be provided for subjects who died, discontinued treatment or withdrew from study due to an AE, or experienced SAEs, and any study procedure-related AEs.

Clinical laboratory data will be summarized by the type of laboratory test and by changes from baseline. Reference ranges and abnormal results (specified in the SAP) will be used in the summary of laboratory and ECG data. The frequency and percentage of subjects who experience abnormal clinical laboratory results (ie, outside of reference ranges) and/or clinically significant abnormalities (as determined by the Investigator) will be presented for each clinical laboratory measurement, including for Hy's Law analysis (ALT, AST, total and direct bilirubin, ALP). Shift tables may be provided for changes from baseline in selected chemistry and hematology laboratory parameters. Listings of abnormal vital signs and physical findings will be provided. The SAP will provide additional details on the planned safety analyses. Several safety laboratory tests will also be examined for efficacy (Section 11.7).

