GSD III is a heterogeneous disorder with variable phenotype depending on the site and functional implication of *AGL* mutation. In turn, clinical characteristics vary depending on the relative extent of liver or muscle involvement, with most patients experiencing consequences of both liver and muscle involvement (Sentner et al., 2016). Patients with GSD III generally present by the age of 1.5 years (Sentner et al., 2016; Van Hoof and Hers, 1967), with hepatomegaly the most common presenting clinical sign. Other hallmarks of the disease include ketotic hypoglycemia with fasting, hyperlipidemia, growth retardation, elevated liver transaminases, and elevated creatine kinase. Some individuals also develop osteoporosis or osteopenia over time (Derks and Smit, 2015). Hepatomegaly may appear to improve with age with a reduced relative glucose requirement; however, it is increasingly recognized that progressive liver cirrhosis and hepatic failure can occur, with some patients developing hepatic adenoma, hepatocellular carcinoma, or end-stage liver cirrhosis (Kishnani et al., 2010). Skeletal and cardiac muscle involvement also varies widely, with reports of asymptomatic cardiomyopathy, symptomatic cardiomyopathy leading to death, ventricular hypertrophy, sudden death due to cardiac arrhythmia, and slowly progressing myopathy with distal, proximal or generalized myopathy.

Four subtypes of GSD III have been described: IIIa, IIIb, IIIc, and IIId. Types IIIa and IIIb are the most common, comprising 85% and 15% of the total incidence, respectively. Types IIIc and IIId are extremely rare, with a combined incidence less than 1% of the GSD III population.

(Kishnani et al., 2010). The incidence of GSD III is approximately 1:100,000 in the United States (US), with higher incidences in some populations including the North African Jewish population (~1:5,400) and in the Inuit population in Nunavik, Canada (~1:2,500) (Rousseau-Nepton et al., 2015; Endo et al., 2006; Parvari et al., 1997; Moses et al., 1973).

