To minimize reporting bias for safety and PD/efficacy assessments, placebo was chosen as the appropriate control for the DB-RD cohorts. Data from this FIH study will provide the basis for the initial safety profile of UX053. Enrolled subjects are expected to have signs and symptoms of GSD III, AEs related to the GSD III, and numerous laboratory abnormalities. Blinded treatment allocation reduces bias in reporting of AEs; the placebo control is helpful to determine whether UX053 exacerbates the underlying disease, or whether the events represent disease progression. Minimizing bias in the safety and PD data from this study is critical to inform the clinical development of UX053. An unbiased assessment of PD endpoints will allow for the identification and prioritization of clinically relevant endpoints in subsequent phases of clinical development.

There are no approved treatments for GSD III. All study participants will receive standard of care in addition to placebo or UX053. In fact, standard of care nutrition management guidelines have been incorporated into the protocol to ensure that standard of care will be followed (Section 7.1). The use of a placebo control will not impact standard of care. Once chronic toxicity data are available, a future protocol amendment is planned to allow all subjects, including those previously treated with placebo, to receive long-term open-label treatment with UX053.

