8.1. Inclusion Criteria

Each subject must meet the inclusion criteria listed below at screening (ISV for DB-RD cohorts) or rescreening (OL-RD cohorts) and baseline (Day 0 for SAD cohorts or Week 0 in all RD cohorts), as applicable, to be enrolled in the study:

1. Confirmed diagnosis of GSD III (all subtypes) based on pathogenic mutations in the *AGL* gene on both alleles or GDE deficiency based on biopsy of liver, muscle, or fibroblasts
2. History of any of the following:
 - a. Severe hypoglycemia, defined as neuroglycopenia (eg, altered mental status, seizure, dizziness, slurred speech, blurry vision, abnormal behavior, perioral paresthesia, requiring intervention by a caregiver) or blood glucose < 54 mg/dL (3 mmol/L) within the last year
 - b. ≥ 2 incidents of symptomatic hypoglycemia (defined as blood glucose < 70 mg/dL [3.9 mmol/L] if measured at the time of symptoms) within the last year, despite nutrition management
 - c. Ongoing liver injury, defined as alanine aminotransferase (ALT) > 2.5 x the upper limit of normal (ULN) within the last year
3. For treatment-naïve subjects (SAD and DB-RD cohorts), ALT ≤ 5 x the upper limit of normal (ULN) during the 3 months prior to the Baseline Visit.
4. Males or females ≥ 18 years of age
5. For subjects enrolling into DB-RD cohorts, willing and able to demonstrate nutrition stability based on nutrition guidelines for adults with GSD III ([Table 2](#))
6. Willing and able to provide access to medical records surrounding medical treatment that occurred prior to enrollment and during the study
7. Willing and able to provide written informed consent, or in the case of adult subjects with cognitive limitation, provide written assent (if required) and written informed consent by a legally authorized representative after the nature of the study has been explained and prior to any test procedures or assessments
8. Females of childbearing potential must have a negative pregnancy test at screening (and rescreening, as applicable) and be willing to have additional pregnancy tests during the study. Subjects of child-bearing potential or males who are sexually active with partners of child-bearing potential must consent to use a highly effective contraceptive method, as described in [Appendix 4](#), from the Period following the signing of the informed consent through 30 days after last dose of study drug

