10.1.5. Safety Laboratory Tests

Blood and urine samples will be collected for safety laboratory tests as specified in [Table 4](#), [Table 5](#), and [Table 6](#). Fasting is not required. For visits in which subjects are receiving study drug, laboratory samples will be collected prior to dosing. All efforts should be made for urine collections to be from the first morning void. Samples will be processed by a central lab to ensure consistency across study sites.

In addition to chemistry, hematology, and urinalysis, additional assessments to monitor safety include activation of the complement pathway, coagulation factors, and interleukin-6. As noted in [Table 4](#), [Table 5](#), and [Table 6](#), samples for complement pathway, coagulation factors, and interleukin-6 are collected pre- and post-infusion. Post-infusion blood samples should be collected in the opposite arm of the infusion to avoid laboratory artefacts. The full list of safety laboratory evaluations to be performed in this study are listed in [Appendix 3](#). All laboratory samples listed in [Appendix 3](#) will be processed by a central laboratory, except urine pregnancy.

The study site should indicate to laboratories if the subject is taking high dose biotin supplements (found in multivitamins, biotin supplements, and some supplements to promote hair, skin, and nail growth) to potential risk of assay interference (eg, troponin) ([FDA, 2019a](#)).

The Investigator (and/or Medical Monitor) may at his/her discretion perform additional laboratory tests for subject safety if a subject experiences an SAE or other AE that may warrant further follow up.

Close monitoring is required for subjects who develop elevations in ALT > 3x ULN and > 2x their baseline value, or elevation in ALT > 3x ULN with INR > 1.5. This includes repeating liver enzymes and INR within 48 hours and consideration of additional diagnostic tests such as liver ultrasound.

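### Protocol 11.4 counts out-of-range laboratory results with no baseline condition, so the ALT and AST counts will partly or largely reflect GSD III and lose sensitivity to a drug effect

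*Protocol*

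**What the plan says.** Protocol 11.4 describes the laboratory analysis in four parts.

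- A general summary: "Clinical laboratory data will be summarized by the type of laboratory test and by changes from baseline".
- A subject-level count, worded as "The frequency and percentage of subjects who experience abnormal clinical laboratory results (ie, outside of reference ranges". No requirement is stated that the result be new or worse than at baseline.
- A companion in the same sentence: "and/or clinically significant abnormalities (as determined by the Investigator) will be presented for each clinical laboratory measurement". The sentence goes on to include the analytes for a Hy's Law analysis, without thresholds.
- An optional display: "Shift tables may be provided for changes from baseline in selected chemistry and hematology laboratory parameters".

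On the population, Protocol 5.1 states: "Other hallmarks of the disease include ketotic hypoglycemia with fasting, hyperlipidemia, growth retardation, elevated liver transaminases, and elevated creatine kinase". Protocol 7.1.3 adds: "Enrolled subjects are expected to have signs and symptoms of GSD III, AEs related to the GSD III, and numerous laboratory abnormalities". One of the three alternative routes under inclusion criterion 2 is "Ongoing liver injury, defined as alanine aminotransferase (ALT) > 2.5 x the upper limit of normal (ULN) within the last year". Inclusion criterion 3 allows ALT up to 5x ULN in treatment-naïve subjects.

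Protocol 10.1.5 asks for close monitoring of "subjects who develop elevations in ALT > 3x ULN and > 2x their baseline value". SAP Section 8 limits the analysis to 4 subjects in Cohort 1S and 4 in Cohort 2S, all on open-label UX053.

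**The concern.** Safety is the primary objective, and hepatotoxicity is one of the three potential risks named in Protocol 5.4.1. The natural question for the liver tests is how many subjects got worse after dosing. The count in 11.4 answers a different one: how many had a result outside the range. Where the disease itself puts ALT and AST out of range, a high count says little about UX053. It could be read as widespread liver toxicity when it is only GSD III, and a real increase in affected subjects would move it little. The 8 subjects analysed have no placebo group against which to judge it.

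**Working it through.** The plan gives no figure for this count, so there is none to reproduce. The check sets the rules side by side and then sizes the loss of sensitivity.

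**1. What the rule does to two illustrative subjects.** Both start at ALT 2.6x ULN, which inclusion criterion 3 allows.

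- Subject A goes to 2.4x ULN: ratio to baseline 2.4/2.6 = 0.92. Outside the range, so counted.
- Subject B goes to 7.9x ULN: ratio 7.9/2.6 = 3.04. Outside the range, so counted.

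The > 3x ULN and > 2x baseline criterion in Protocol 10.1.5 separates them: B meets both limbs, A meets neither.

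**2. Rules used elsewhere in the same documents.** A TEAE must be new or worsened (Protocol Appendix 1, SAP 7.7). The marked-increase rule in Protocol 8.3.2 and the transaminase criteria in 8.3.3 all refer to the subject's own baseline. SAP 7.11.2 counts QTc increases from baseline of > 30 and > 60 ms and commits to ECG shift tables. The laboratory out-of-range count is the one without a baseline reference.

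**3. Size.** Inputs:

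- N = 8 subjects (SAP Section 8).
- q = share already out of range at baseline. Not in the documents, so assumed across the whole range.
- p = risk of a new abnormality on drug in a subject in range at entry. Assumed 20%.
- No new abnormalities without the drug (a simplification).

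Expected count with no drug effect = 8q. Expected count with a drug effect = 8[q + (1 − q)p]. Chance that at least one subject is newly abnormal = 1 − [1 − (1 − q)p]^8.

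| q | Count, no drug effect | Count, drug effect | Chance of at least 1 newly abnormal |
|---|---|---|---|
| 0% | 0 | 1.6 | 83% |
| 25% | 2.0 | 3.2 | 73% |
| 50% | 4.0 | 4.8 | 57% |
| 75% | 6.0 | 6.4 | 34% |
| 90% | 7.2 | 7.36 | 15% |
| 100% | 8 | 8 | 0% |

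For example, at q = 75%: 8 × (0.75 + 0.25 × 0.20) = 6.4, and 1 − (1 − 0.05)^8 = 0.337.

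The drug's contribution to the count is 8(1 − q)p, so it shrinks in proportion to 1 − q. A count of worsening to which all 8 subjects can contribute, at the same 20% risk, stays at 1 − 0.8^8 = 83% whatever q is. With p = 50% the pattern is the same: at q = 75% the counts are 7.0 against 6.0, and the chance is 66% rather than 99.6% at q = 0.

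**The case against.** The strongest reply is that this count is not the only laboratory display, and that is right. Change from baseline is committed to without condition, and Protocol 11.3.1 and SAP 7.1 specify minimum and maximum as well as mean and median. With 4 subjects per cohort, the maximum shows the worst single rise. SAP 7.1 also promises listings of raw CRF data and subject-level graphs of endpoints. A rise such as 2.6x to 7.9x ULN would trigger repeat testing under Protocol 10.1.5. The Investigator may well judge it clinically significant (Appendix 2), and it would then be recorded as an adverse event and enter the primary endpoint. All of this stands, and it means a large rise would not be hidden. But the maximum describes one subject, and the Investigator-based counts rest on judgement in patients expected to be abnormal. None gives an objective number of subjects who worsened.

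Four stronger readings that a reader might infer are not supported:

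- **That the count cannot show a drug effect.** Raised ALT is only one of three entry routes and may date from any time in the previous year; criterion 3 is a ceiling. Subjects in range at entry can still become abnormal, and the DB-RD cohorts were planned with placebo. Only at q = 100% is the count wholly uninformative.
- **That the Hy's Law transaminase limb is a fixed multiple of ULN.** Section 11.4 sets no multiple, and the combined liver criterion in 8.3.3 already requires > 2x baseline.
- **That HDL and LDL counts are affected in the subjects analysed.** Protocol Table 4 schedules neither after dosing in the SAD cohorts. Of the lipids, only total cholesterol and triglycerides, in the chemistry panel, could be.
- **That the SAP omits a treatment-emergent definition.** Protocol 11.4 defers the abnormal-result criteria to the SAP. The readable SAP has no laboratory section, but large parts of it are redacted, so no omission can be claimed.

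**Conclusion.** The point holds for the rule as written in Protocol 11.4, and mainly for ALT and AST. The count has no stated baseline condition, the disease is expected to put these tests out of range, and the subjects analysed have no comparator. The count will therefore partly or largely describe GSD III. If 50%, 75% or 100% of subjects are assumed abnormal at baseline, 4, 6 or 8 of 8 are counted with no drug effect, leaving 4, 2 or 0 in whom the count could rise. Those shares are assumptions, and a lower share makes the problem smaller. The other displays limit the harm to the lack of an objective count of subjects who worsened. This is more than a missing detail, because the rule is stated and changing it changes the reported numbers. It is worth correcting, but it does not show that a liver signal would be missed.

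**What to change.** In Protocol 11.4:

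- Replace the out-of-range count with treatment-emergent abnormality: in range at baseline and out of range after dosing, or a worse CTCAE grade than at baseline.
- Add a table category for ALT and AST using the existing > 3x ULN and > 2x baseline criterion. This is for display only and changes no monitoring or stopping rule.
- Make shift tables definite for ALT, AST, ALP, GGT, bilirubin, INR and platelets. INR has to be named, because Appendix 3 lists it outside the chemistry and hematology panels to which the optional shift tables apply.

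If the redacted SAP text already contains these rules, a cross-reference from 11.4 is enough. The cost is protocol or SAP wording and a few lines of table programming, with no new data.

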11.5. Pharmacokinetic Analyses

PK parameters will be derived by non-compartmental analysis. PK parameters to be estimated may include, but not limited to, the following: T_{max} , C_{max} , AUC_{last} , AUC_{inf} , AUC_{tau} , $RAUC$, T_{last} , $T_{1/2}$, CL , and V_{ss} . PK parameters will be descriptively summarized by dose levels and time in SAD and RD, respectively. The SAP will provide additional details on PK analyses.

11.6. Anti-drug Antibody Analyses

The incidence and titer for ADA to **CCI** [REDACTED] and GDE will be evaluated and summarized for each subject at time points specified in [Table 4](#), [Table 5](#), and [Table 6](#). Samples may be stored for further assessment to evaluate the presence of neutralizing antibodies.

11.7. Efficacy Analyses

Efficacy parameters will be summarized at screening (or rescreening, as applicable) and baseline (or both), and at each observed time point that the assessment is collected thereafter, as specified in [Table 4](#), [Table 5](#), and [Table 6](#); change from screening (or rescreening, as applicable) or baseline (or both) will also be summarized where applicable. Several laboratory tests examined for safety will also be considered for efficacy (Section [11.4](#)). Additional details regarding tertiary and exploratory endpoint analysis are available in the SAP.

11.8. Nutrition Diary

Data from the nutrition diary will be summarized with descriptive statistics. Additional details regarding analysis of the nutrition diaries are available in the SAP.

11.9. Exploratory Analyses

Details regarding exploratory analyses are available in the SAP.

11.10. Planned Subgroup Analyses

If a sufficient number of subjects with different disease subtypes are enrolled, subgroup summaries by disease subtype will be provided. Additional details regarding potential subgroup analysis are available in the SAP.

11.11. Planned Analyses

Analyses are planned for each data review described in the study design (Section [7.1](#)). For the SAD cohorts, Ultragenyx will review at least 2 weeks of safety data for all subjects within a cohort before deciding to proceed with the next SAD cohort. For the RD cohorts, an unblinded DMC will review either at least 6 weeks of safety from at least 4 subjects in a DB-RD cohort or 12 weeks of safety data from at least 3 subjects in an OL-RD cohort (whichever is available first) before providing a recommendation for proceeding with repeat dosing at the next dose level. All available data from prior cohorts will also be reviewed when considering proceeding with new cohorts.

11.12. Data Monitoring Committee

An independent DMC will be constituted with experts in metabolic liver disease, GSD III, and/or immune activation and will act in an advisory capacity to Ultragenyx. Additionally, at least 1 of the DMC members will have expertise concerning statistical methods used in the design and analysis of clinical trials.

The DMC will meet and review study data at the frequency defined and in accordance with the scope and objectives set forth in the DMC Charter. The DMC may provide advice to Ultragenyx regarding the safety of subjects, the ethics of the study and the continuing scientific validity of the study. The DMC may also make recommendations to Ultragenyx concerning continuation, termination or other modifications of the study based on their review of data. Further details regarding the DMC can be found in the DMC charter, which will be available prior to the administration of IP.

Ultragenyx will review the DMC recommendations and determine necessary actions that will be communicated accordingly to all stakeholders, eg, Regulatory Authorities, IRBs/IECs, and Investigators.

